Exploratory Aim: To examine whether symptom severity, social anxiety, mood, attachment style, and rejection sensitivity moderate the effects of oxytocin.

III. Subject Selection

Inclusion Criteria for BDD Groups:

1. Treatment-seeking adult males and females \geq 18 years of age
2. Meets DSM-IV criteria for principal BDD as determined by Structured Clinical Interview for DSM-IV (SCID) diagnostic interview
3. For females only: must be using low-dose hormonal contraceptives, as defined by <50 mcg daily dose of ethinyl estradiol. Female participants will bring medication labeling to the screening visit so study staff may verify acceptable drug composition.

Exclusion Criteria for BDD Groups:

1. Current diagnosis of schizophrenia, psychotic disorder, bipolar disorder, substance abuse or substance dependence. All other Axis I comorbidities will be permitted to foster the accrual of a clinically relevant sample.
2. Significant nasal pathology (e.g., atrophic rhinitis, history of hypophysectomy, recurrent nosebleeds)
3. Smokers who smoke \geq 15 cigarettes daily
4. Serious medical illnesses (including untreated thyroid disease, diabetes, cardiovascular disease, and seizures, as assessed by medical history). Individuals who are taking levothyroxine or who report a history of thyroid disease will be given a blood test to determine thyroid hormone levels and eligibility for the study.
5. Active homicidal or suicidal ideation
6. Steroid or hormone use (except low-dose contraceptives for females, which is allowed)
7. For females only: positive urine pregnancy test and use of high dose contraceptives (low dose contraceptives will be allowed due to stability of hormone levels during active phase)

Inclusion Criteria for Control Participants:

1. Adult males and females \geq 18 years of age
2. No current DSM-IV Axis I diagnosis, as determined by SCID
3. For females only: must be using low-dose hormonal contraceptives, as defined by <50 mcg daily dose of ethinyl estradiol. Female participants will bring medication labeling to the screening visit so study staff may verify acceptable drug composition.

Exclusion Criteria for Control Participants:

1. Current diagnosis of any DSM-IV Axis I disorder
2. Significant nasal pathology (e.g., atrophic rhinitis, history of hypophysectomy, recurrent nosebleeds)

3. Smokers who smoke \geq 15 cigarettes daily

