The study will consist of 3 study visits in total. The first visit will involve the diagnostic assessment and medical screen to determine eligibility for the study, in addition to the administration of clinician-administered and self-report questionnaires. This visit will take approximately 2.5 hours to complete. If participants are eligible, they will be asked to return to the clinic for two additional study visits, which will be identical in procedure and take approximately 2 hours each to complete. Female participants must complete Visits 2 and 3 during the active phase of their contraceptive medication (e.g. not during their menses); female subjects using multiphasic contraceptives must be on the same dose of ethinyl estradiol for both Visit 2 and 3. Participants will be instructed to avoid alcohol, caffeine, and nicotine for 24 hours prior to Visits 2 and 3. These visits will involve the administration of both an oxytocin and placebo nasal spray, in randomized order, and the completion of various social cognition tasks. They will be separated by a one-week washout period (**maximum 28 day** window period). The study design and procedures are represented in the following schematic:

[figure not shown]
Diagnostic Assessment and Medical Screen:

After obtaining informed consent, participants will be administered the Structured Clinical Interview for DSM-IV (SCID-I/P; First, Spitzer, Gibbon, & Williams, 2002) to determine diagnostic eligibility. The SCID allows the investigator to assess all diagnostic inclusion and exclusion criteria. Participants who are recruited for the healthy control

group will be given the SCID-I/P to confirm the absence of Axis I psychopathology. Participants who meet the diagnostic inclusion and exclusion criteria will be given a medical screen consisting of a history and physical examination (H&P) by a study nurse or physician to determine the participant's eligibility and safety for the study. In addition, a urine pregnancy test will be given to females during this visit, as well as at the beginning of Visits 2 and 3 to ensure continued eligibility.

Investigational Agent (dose, method, schedule of administration, dose modifications):

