Mini-Markers Scale (MM; Saucier, 1994): The Mini-Markers Scale is a 40-item self-report measure of the five factor model personality factors: extraversion, agreeableness, conscientiousness, emotional stability, and openness. It asks participants to rate how accurately each item describes themselves on a 1-9 point Likert scale ranging from "extremely inaccurate" to "extremely accurate."

Adverse Events Form: This self-report form will be administered at Visits 2 and 3 after nasal spray administration to assess for any adverse events. Participants will be asked to report on a symptom checklist whether they experienced a negative reaction to the oxytocin and placebo nasal sprays. If participants endorse 'yes' on any item, a study clinician or nurse will follow up and ask them whether the symptom resolves by the end of the study visit.

Assessment of Blind Form: This questionnaire will be given at Visits 2 and 3 after nasal spray administration to assess for participants' expectancies regarding the drug they received. Participants will be asked which nasal spray they believe they received (oxytocin or placebo), to rate their degree of certainty, and to describe their reasons why.

Tasks:

The following tasks will be administered at each study visit approximately 45 minutes after drug administration. The order of tasks will be the same within each participant in the study between Visit 2 and Visit 3 in order to minimize variance for the within-subject analysis and isolate the effect of the drug. However, the order of tasks will be counterbalanced between participants in the study, to account for possible carry-over effects.

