5. **Unexpected adverse event** means any *adverse event* occurring in one or more subjects participating in a research protocol, the nature, severity, or frequency of which is not consistent with either: (1) the known or foreseeable risk of adverse events associated with the procedures involved in the research that are described in (a) the protocol-related documents, such as the IRB-approved research protocol, any applicable investigator brochure, and the current IRB-

approved informed consent document, and (b) other relevant sources of information, such as product labeling and package inserts; or (2) the expected natural progression of any underlying disease, disorder, or condition of the subject(s) experiencing the adverse event and the subject's predisposing risk factor profile for the adverse event.

Reporting Requirements:

According to the PHRC adverse events reporting policy, PIs are required to report unanticipated problems that occur during the conduct of the study, after study completion, or after subject withdrawal or completion, to be submitted within 5 working days/7 calendar days of the date the PI first becomes aware of the problem. Specifically, reports of unanticipated problems involving risks to subjects or others are to be submitted through Insight/eIRB within 5 working days/7 calendar days of the date the PI first becomes aware of the problem.

Internal adverse events that are **unexpected** and **related/possibly related** to the research and **external** adverse events that are **serious, unexpected and related/possibly related** must be reported to the IRB within 5 working days/7 calendar days of the date the PI first becomes aware of them. Any less serious, expected (e.g., documented in the protocol), or unlikely related adverse events will be reported to the IRB as part of its yearly continuing review process.

Adverse events to be **expected** in the current study, based on Syntocinon® Basic Prescribing Information, previously published data, and from participants in the study to date, include:

- Headaches
- Nausea
- Allergic dermatitis
- Uterine contractions
- Lightheadedness
- Nasal irritation
- Dry mouth/throat
- Feeling of calmness or euphoria
- Anxiety or depression
- Feeling drowsy or sleepy
- Difficulty sitting still
- Trouble concentrating
- Tremors or shakiness

X. References

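### The adverse-event checklist is described only after the spray, so a symptom present on arrival can be recorded as a spray reaction with nothing described to separate the two

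*Combined protocol and SAP*

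**What the plan says.** Section V, Self-Report Questionnaires, sets the timing of the Adverse Events Form: "This self-report form will be administered at Visits 2 and 3 after nasal spray administration to assess for any adverse events". Its content is an attribution question: "Participants will be asked to report on a symptom checklist whether they experienced a negative reaction to the oxytocin and placebo nasal sprays". If any item is endorsed, "a study clinician or nurse will follow up and ask them whether the symptom resolves by the end of the study visit". The text mentions no question on when the symptom began.

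The Overview of Study Procedure places symptom questionnaires at the first visit, "in addition to the administration of clinician-administered and self-report questionnaires". For the dosing visits it adds an abstinence instruction: "Participants will be instructed to avoid alcohol, caffeine, and nicotine for 24 hours prior to Visits 2 and 3".

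The BDD exclusion criteria in Section III rule out psychotic disorders, bipolar disorder and substance abuse or dependence, then state: "All other Axis I comorbidities will be permitted to foster the accrual of a clinically relevant sample". Controls may have no current Axis I diagnosis.

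Section IX (Definitions) counts an adverse event whether or not it is thought to be related to the research. Under Reporting Requirements, the list of expected events draws on prescribing information, published data and reports "from participants in the study to date". Expected events go to the IRB at yearly continuing review. Internal events that are unexpected and at least possibly related go within 5 working days/7 calendar days.

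**The concern.** A checklist completed once, after dosing, records what is present then. It cannot show what was present before. Several items on the expected list (anxiety or depression, drowsiness, difficulty sitting still, trouble concentrating, headaches) are complaints a participant could bring to the visit, and the two groups are selected to differ in psychiatric comorbidity.

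Three things are at stake. A single participant's symptom cannot be classed as new or old from the form as described. Absolute rates after each spray, and any description of tolerability in BDD against controls, can mix background with reaction. Study reports may also feed the expected list, which helps decide how quickly later events are reported.

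**Working it through.** The plan states no figure on this point, so there is none to reproduce. The check is a reading of the text followed by an illustration.

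**Reading**

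1. Before the spray: the only check described at the start of Visits 2 and 3 is a urine pregnancy test. Symptom questionnaires belong to Visit 1, and Methods of Enrollment allows them to be taken from another study up to six months earlier. No same-day symptom baseline is described.
2. After the spray: the checklist, then resolution by the end of the visit. Onset is not asked.
3. Expected list: Section IX has 13 entries. Section VII already names 8 of these (headaches, nausea, allergic dermatitis, uterine contractions, lightheadedness, nasal irritation, dry mouth/throat, calmness). The other 13 − 8 = 5 are anxiety or depression, drowsiness, difficulty sitting still, trouble concentrating, and tremors or shakiness. These are the items most easily confused with existing complaints. The documents do not give the source of any single item.

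**Illustration (all rates are assumptions)**

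- b: share of visits with the symptom before the spray (10%, 30%, 50%), equal at both visits.
- w: share of those existing symptoms endorsed as a reaction (0, 0.5, 1).
- s: rate of true reactions where no existing symptom is endorsed, 15% after oxytocin and 5% after placebo.

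Recorded rate R = bw + (1 − bw)s. Difference = (1 − bw)(15% − 5%). Share of oxytocin records that are pre-existing = bw / R. For b = 0.10 and w = 1: 0.10 + 0.90 × 0.15 = 23.5% and 0.10 + 0.90 × 0.05 = 14.5%.

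| b | w | Oxytocin | Placebo | Difference (points) | Ratio | Pre-existing share |
|---|---|---|---|---|---|---|
| any | 0 | 15.0% | 5.0% | 10 | 3.0 | 0% |
| 10% | 0.5 | 19.25% | 9.75% | 9.5 | 1.97 | 26% |
| 30% | 0.5 | 27.75% | 19.25% | 8.5 | 1.44 | 54% |
| 50% | 0.5 | 36.25% | 28.75% | 7.5 | 1.26 | 69% |
| 10% | 1 | 23.5% | 14.5% | 9 | 1.62 | 43% |
| 30% | 1 | 40.5% | 33.5% | 7 | 1.21 | 74% |
| 50% | 1 | 57.5% | 52.5% | 5 | 1.10 | 87% |

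**What a pre-spray reading changes**, with w = 1 and the planned 40 participants all completing both visits:

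- Recorded events, 40R: 9.4 vs 5.8, 16.2 vs 13.4, 23 vs 21. Excess on oxytocin: 3.6, 2.8, 2.
- New events only, 40(1 − b)s: 5.4 vs 1.8, 4.2 vs 1.4, 3 vs 1. Excess: 3.6, 2.8, 2.

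The expected excess in counts is the same either way. The pre-spray reading restores the absolute counts, the ratio of 3.0, and the 10-point difference among visits free of the symptom on arrival.

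**By group**, if background were 30% in BDD and 10% in controls with identical spray effects and w = 1: the gap is 40.5 − 23.5 = 17 points after oxytocin and 33.5 − 14.5 = 19 points after placebo. All of it comes from background.

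**The case against.** The strongest reply is the crossover. Every participant completes the same form after placebo, so stable background cancels on average, and the counts above show that the expected oxytocin excess survives without a baseline. A reader might infer that the plan will produce a false oxytocin harm signal. The documents do not support that unless background or endorsement differs between the two visits.

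Other parts of the reply also stand:

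- The form asks about a reaction to the spray, so a participant who arrived with a headache may rightly answer no. It would be wrong to say that existing symptoms are recorded as reactions as a matter of course; they can be. The figures with w = 1 are upper cases.
- That BDD participants will appear to tolerate the spray worse is also too strong. They may, but Section VI plans no adverse-event comparison by group.
- The documents do not show that background symptoms have entered the expected list. Expectedness also turns on severity and frequency, and on the natural progression of the participant's disorder. Serious events reach the DSMB within 24 hours, unblinded, whether expected or not.
- Nothing in the documents says that 24 hours without caffeine or nicotine causes the listed symptoms. Any such contribution is an assumption, and the point does not need it.
- The checklist, the attached administration protocol and the visit schematic are not in the text available, so an onset item cannot be excluded.

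The reply does not reach the individual record. The placebo visit is a different day and cannot show whether a symptom on the oxytocin visit was new. Study staff other than the pharmacy are blinded, and follow-up by a clinician or nurse is described only as a question about resolution. Leaving attribution to the participant also sits poorly with a definition of adverse event that ignores cause.

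**Conclusion.** The point holds in a limited form. As described, the form can record symptoms present on arrival as spray reactions, and nothing described separates them from new ones. The consequences are uncertain individual attribution, inflated absolute rates after both sprays, a BDD-versus-control description that may reflect the disorder, and loss of contrast if a true difference exists.

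The size cannot be known from the documents. It runs from none (no existing symptom endorsed) to a fall in the recorded difference from 10 points to 9, 7 or 5 (all endorsed, background 10%, 30% or 50%). These figures assume true rates of 15% and 5% and equal background at both visits. The only side-effect rate in the protocol is a pooled one, 279 of 1,529 (18%) across oxytocin and placebo recipients in earlier studies, with no detectable difference between them, so the assumed contrast is illustrative.

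The link to the expected list is a possibility, not a finding. The trial's cognitive outcomes are unaffected. This is a cheap improvement to safety data collection.

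**What to change.** At Visits 2 and 3, give the same symptom checklist, with a severity rating, just before the spray as well as after it. Keep recording every event regardless of cause, as the Section IX definition requires. Flag as treatment-emergent those items that are new or rated worse than before the spray, and report them by spray and by diagnostic group. When adding items to the expected list from this study's own reports, use only the flagged ones. If the checklist already records onset, say so in Section V.

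The cost is a short protocol addition and about two minutes per visit (an estimate) with an existing self-report form. Dosing, blinding and endpoints do not change. The downside is that asking beforehand may prompt slightly more symptom reporting, at both visits.

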For all analyses, we will include concomitant medication use as a covariate, in order to control for the effect of concomitant medications on study results. We will also compare participants who are taking psychotropic medications from participants who are not, on

demographic and clinical variables, to ensure there are no systematic differences between these groups.

Power and Sample Size:

Given the novelty of our approach, no background data on the effects of oxytocin in BDD exist to inform the power calculation. Therefore, the proposed sample size of 40 participants (20 per group) was chosen based on feasibility. With 20 participants per group and a two-sided alpha=0.05, for our primary pair-wise comparison (BDD vs. healthy controls) of the mean within-subject difference (oxytocin vs. placebo) in Emotion Recognition Task total score and Trust Game "back transfer" amount, we will have 81% power to detect a moderate effect size of $f=0.23$.

VII. Risks and Discomforts

Oxytocin-Related Risks and Side Effects:

Between 1990 and 2010, there have been 38 controlled studies involving intranasal delivery of oxytocin (MacDonald et al., 2011). A total of 1,529 participants have received intranasal oxytocin or placebo, and nine studies have included participants (N=182) who had a developmental, medical, or mental health disorder. The dosage of oxytocin has typically been a single dose ranging from 20 international units (IU) to 40 IU. Out of the 1,529 participants who have received intranasal oxytocin or placebo, 279 (18%) reported mild side-effects (MacDonald et al., 2011). The most common side-effect was a feeling of calmness, but this did not differ between those who received oxytocin or placebo. A recent review of studies using intranasal oxytocin supported the short-term use of oxytocin, demonstrating that oxytocin produced minimal side-effects, no detectable differences in side-effects between oxytocin or placebo recipients, no subjective changes in recipients, and is equally safe to use with vulnerable populations as with healthy adults (MacDonald et al., 2011). The proposed study intends to use a single 24 IU dose of intranasal oxytocin, which has been the most commonly used dose in previous trials (25 out of 38 studies).

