Data gathered from this study may benefit other individuals with BDD in the future. To date, no studies have examined the oxytocin system in BDD. Given the mounting evidence for oxytocin's role in social and cognitive deficits in autism spectrum disorders, schizophrenia, and other disorders, it is clear that the effects of oxytocin have transdiagnostic implications. Our findings may show that a single administration of intranasal oxytocin may alter social cognitive processes thought to maintain BDD. More importantly, if study aims are achieved, we may learn how to improve treatments for BDD, and identify individuals who would be responsive to oxytocin. Thus, the current study represents a translational approach to investigating potential pathophysiological mechanisms underlying BDD, and will advance knowledge regarding the potential of a promising novel therapeutic agent for BDD.

IX. Monitoring and Quality Assurance

Data and Safety Monitoring Plan:

The study will be monitored for quality assurance and adherence to the protocol according to the following monitoring plan:

A Data Safety and Monitoring Board (DSMB) will be formed consisting of three members who are not associated with the study. The purpose of the DSMB is to: (1) review all adverse events, (2) assess the timeliness, completeness, and quality of the data collected, (3) assess the adherence to protocol requirements, especially measures taken to protect participant safety, and (4) assess the benefit/risk ratio of study procedures. The DSMB will meet once after 40 subjects have been enrolled, and will be provided with the following data prior to this meeting: (1) all adverse events reported, and (2) subject recruitment, enrollment, and dropout numbers. During the meeting, the board will review these data and have 30 days to generate a report, which reflects their opinion of whether the study should be permitted to continue and whether any changes need to be made. This report will then be submitted to the IRB. If any serious adverse events occur during the study, DSMB members will be apprised of them within 24 hours of the event and will be provided unblinded information with regard to the participants' treatment assignment and corresponding study visit. DSMB members will then provide suggestions for the progress of the study, as well as determine whether modifications to the protocol are needed.

Adverse Event Reporting Guidelines:

Definitions:

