1. **Adverse event** means any untoward or unfavorable medical occurrence in a human subject, including any abnormal sign (for example, abnormal physical exam or laboratory finding), symptom, or disease, temporally associated with the subject's participation in the research, whether or not considered related to the subject's participation in the research (modified from the definition of adverse events in the 1996 International Conference on Harmonization E-6 Guidelines for Good Clinical Practice).
2. **Serious adverse event** means any event temporally associated with the subject's participation in research that meets any of the following criteria:
 - results in death;
 - is life threatening (places the subject at immediate risk of death from the event as it occurred);
 - requires inpatient hospitalization or prolongation of existing hospitalization;
 - results in a persistent or significant disability/incapacity;
 - results in a congenital anomaly/birth defect; or
 - any other adverse event that, based upon appropriate medical judgment, may jeopardize the subject's health and may require medical or surgical intervention to prevent one of the outcomes listed above (examples of such events include allergic bronchospasm requiring intensive treatment in the emergency room or at home, blood dyscrasias or convulsions that do not result in inpatient hospitalization, or the development of drug dependency or drug abuse).
3. **Unanticipated problem involving risks to subjects or others** means any incident, experience, information, outcome, or other problem that is *unexpected* and related to the research, and that indicates that the research places subjects or others at an increased risk of physical, psychological, economic, legal, or social harm than was previously known or recognized.
4. **Unexpected** means that the incident, experience, or outcome is unexpected (in terms of nature, severity or frequency) given the (a) research procedures that are described in the protocol- related documents, such as the IRB-approved research protocol and informed consent document and (b) the characteristics of the study population being studied.

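### As described, the Adverse Events Form asks about negative reactions to the spray, which is narrower than the protocol's cause-neutral definition of an adverse event

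*Combined protocol and SAP*

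**What the plan says.** Section V (Self-Report Questionnaires, Adverse Events Form) gives the form a broad purpose: "This self-report form will be administered at Visits 2 and 3 after nasal spray administration to assess for any adverse events". The next sentence describes what participants are asked: "Participants will be asked to report on a symptom checklist whether they experienced a negative reaction to the oxytocin and placebo nasal sprays". Staff involvement then depends on the answer: "If participants endorse 'yes' on any item, a study clinician or nurse will follow up and ask them whether the symptom resolves". Resolution is judged before that visit closes.

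Section IX (Adverse Event Reporting Guidelines, Definitions, item 1) defines an adverse event by its timing relative to participation, "whether or not considered related to the subject's participation in the research". Section IX (Reporting Requirements) then sorts events by whether they are unexpected and related or possibly related, and it keeps the remainder in view: "Any less serious, expected (e.g., documented in the protocol), or unlikely related adverse events will be reported to the IRB" at yearly review. Its list of expected adverse events includes "Feeling of calmness or euphoria". Section IX (Data and Safety Monitoring Plan) supplies the DSMB with "all adverse events reported".

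**The concern.** The definition leaves cause out of the question of what counts as an adverse event. Relatedness is judged afterwards, when an event is sorted for reporting. The form, as described, puts a causal judgement first and gives it to the participant: a reaction to a spray is a symptom that the participant attributes to the spray. It adds a second condition, that the reaction be negative.

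This trial gives participants plausible reasons to attribute symptoms elsewhere. Section V asks them to go without caffeine and nicotine for the day before each dosing visit, and Section III admits smokers of fewer than 15 cigarettes a day. Dosing visits last about two hours and are filled with tasks. The expected list includes headache, drowsiness, anxiety or low mood, restlessness and poor concentration. Any of these could be put down to abstinence, to fatigue or, in the patient group, to the disorder itself.

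What is at stake is completeness of safety ascertainment. A symptom that the participant screens out triggers no follow-up, receives no relatedness judgement and is absent from what the IRB and the DSMB see. It cannot readily be recovered later.

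**Working it through.** No sample size, power or event-count formula bears on this point, and the plan states no figure to reproduce. The check is a comparison of texts.

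1. **Purpose against question.** The form's purpose (Section V) carries no limit by cause. The question described in the following sentence has two limits, cause and unpleasantness. The question is therefore narrower than the form's own purpose.

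2. **Question against definition.** Section IX, Definitions, item 1 requires an untoward occurrence linked in time to participation and sets cause aside. An unpleasant headache that a participant blames on missed caffeine meets the definition. Read literally, the question does not ask for it.

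3. **Question against the expected list.** Section IX lists "Feeling of calmness or euphoria" among expected adverse events. Section VII, summarising a review of earlier intranasal studies, reports: "The most common side-effect was a feeling of calmness", with no difference between oxytocin and placebo. A participant who felt pleasantly calm has no natural reason to report a negative reaction.

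4. **What happens after a missed symptom.** Follow-up begins only with a positive answer, and the one question described is whether the symptom resolves. No step for recording severity or relatedness is described at the visit, although the Section IX sorting needs a relatedness judgement. Events judged unlikely to be related are meant to reach the IRB each year, and the DSMB is meant to see what was reported, with no relatedness filter. A symptom not endorsed reaches neither.

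5. **Other routes.** A blinded nurse is present while the spray is taken (Section V, Oxytocin and Placebo Administration), but no symptom inquiry by that nurse is described. Serious adverse events go to the DSMB within 24 hours (Section IX), which does not cover ordinary symptoms. No other routine, cause-neutral inquiry is described for Visits 2 and 3 or for the interval between them.

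6. **Effect on planned analyses.** Section VI specifies regressions for the task and questionnaire outcomes and for moderators. It plans no comparison of adverse events between oxytocin and placebo. Nothing in the efficacy analysis or the power statement depends on this form.

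Steps 1 to 3 establish the mismatch. Steps 4 and 5 show that nothing described makes up for it. Step 6 limits its reach. The direction of any error is towards fewer recorded events.

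**The case against.** The strongest reply is that one summary sentence is being asked to bear too much. The form is not reproduced, its stated purpose is broad, and it is a checklist answered item by item. Such a checklist may well elicit symptoms whatever their cause. This stands as a limit on the claim: the documents show how the form is described, not how it reads. It does not remove the mismatch, because the description conflicts with the purpose stated one sentence before it.

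A second reply is that asking for negative reactions fits a definition confined to untoward or unfavourable occurrences, so a pleasant feeling need not be collected. That is fair as far as the definition goes, and part of the tension lies between the definition and the expected list. But having listed calmness or euphoria as an expected adverse event, the protocol needs a question that can pick it up.

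A third reply is that the expected list draws partly on participants already studied and contains mood and concentration items absent from the Section VII risks, which suggests wider capture in practice. The list does not say which source supplied which item, so this is suggestive only.

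Two stronger readings are tempting, and neither is supported:

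- **Participants' guesses about cause or spray determine which events are counted, biasing oxytocin against placebo.** The form is not said to be the sole source of events. The question covers both sprays, so a participant who believes the spray was placebo is still asked. Participants and staff outside the research pharmacy are blinded. A difference between conditions would require attribution to follow the participant's guess and the guess to track the actual spray; the documents give no evidence of this, though they do not exclude it. No planned safety comparison exists to be biased.
- **A number of lost events can be derived from Section VII.** The rate there is 279/1,529 = 18.2%. It is a proportion of participants in other studies, given oxytocin or placebo, who reported mild side effects. Multiplying it by 40 × 2 = 80 dosing sessions treats a per-participant rate as a per-session rate. The rate may itself already reflect attribution. The share of symptoms not blamed on the spray appears nowhere in the documents, so any count of losses would rest on an invented fraction.

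**Conclusion.** The point holds as an inconsistency in safety ascertainment. The only routine adverse-event tool described for the dosing visits is narrower, as described, than its own purpose and than the protocol's definition. Events that the protocol means to count can go unrecorded before anyone qualified judges relatedness.

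The size of any under-count cannot be calculated from the documents. The conclusion that events can be missed assumes that the actual form follows its description. If the form is already cause-neutral, the defect shrinks to one inaccurate protocol sentence. On either assumption the passages need to be reconciled. The efficacy analyses and the power statement are untouched.

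**What to change.** Reword the form, and the sentence in Section V that describes it, so that for each checklist symptom the participant is asked whether it occurred since the spray, whatever the participant thinks caused it. Make sure that the checklist contains every event on the Section IX expected list, including calmness or euphoria. Have the blinded study clinician or nurse who already follows up each positive answer record relatedness as a separate item, so that the Section IX sorting rests on a clinical judgement.

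The cost is one revised form, one revised protocol sentence, one added follow-up item and a few more unrelated symptoms to review. Because Section IX refers to participants already studied, record the date of the change and avoid switching forms between a participant's two dosing visits, so that both are ascertained in the same way.
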